5.4.2 AVAILABILITY OF CASES AND JUSTIFICATION OF SAMPLE SIZE

A review of cancer registry data shows that the 2 participating hospitals treated 313 PCa cases in 2001 of which 150 cases were identified as being of African-American and 143 cases as being of Caucasian descent (Table 8). Twenty cases were either not informative for race or had a different race/ethnic background (e.g., Asian, Hispanic). Most of the cases had residency in the greater Baltimore area. There were 52 known available cases with radical prostatectomy in 2001, which is sufficient to meet our goal of recruiting at least 25 cases with radical prostatectomy per year.

We will use the case-control design to detect statistically significant differences in the frequency of genotypes between PCa patients and randomly selected population-based controls that are matched by age, gender and race to the cases. For the initial analysis, all cases will be grouped together. We will then examine the study population stratified by race and/or exposure. The study is designed to detect risk associations that have odds ratios of ≥ 1.5 . Associations between PCa and genotypes of the angiogenesis and hormone pathways have been found to have odds ratios that are in the range of 1.5-2.5 (39,69-71). Examples are shown in Table 3. We are not aiming to detect weak risk associations that are reflected by odd ratios between 1 and 1.5. Such associations are prone to a selection bias and confounding, and would require a larger sample. Our proposed study is exploratory and designed to detect potentially novel genotype–cancer risk associations. The finding of a new disease-associated genotype can subsequently be validated in a larger study.

Known Available Cases by Hospital Calendar Year 2001					
	African-American Caucasian Total				
VA Hospital	85	48	133		
All Cases					
UM Medical Center	65	95	160^{-1}		
All Cases					
Total	150	143	293		
1 >70% of patients are from the greater Baltimore area					

Table 8: Known Available Cases from Hospital Tumor Registries

POWER CALCULATIONS

The power calculation assumes a study size of 400 cases and 400 controls which was the study size in the originally approved protocol. The study size was subsequently increased to 600/600 after approval of an amendment in 2006 to 1000/1000 after approval of an amendment in 2010. Power calculations were performed with the Power and Sample Size (PS) software, Version 2.1.30. William D. Dupont and Walton D. Plummer at the Vanderbilt University Medical Center have developed this software to conduct power calculations for clinical and epidemiological studies. The program is available on the Internet at http://www.mc.vanderbilt.edu/prevmed/ps/.

ANALYSIS OF ALLELE VARIANT GENES WITH ALL CASES GROUPED TOGETHER

We assume 1) a study population of 400 cases and 400 controls, and 2) two-sided alpha = 0.05, and 3) a prevalence of 5%, 20% or 40% for the disease-associated allele. We selected the candidate allele variants using the following criteria (and/or): 1) the allele variant gene is functionally important (literature), and 2) the polymorphism will likely affect protein expression/stability/activity or mRNA splicing/stability, and 3) the frequency of the rare allele is greater 5% in the general population. The power to detect an association between an allele variant and cancer risk at a given odds ratio is shown in Table 9.

Table	9
I GOIC	

Odds	5% Prevalence	20% Prevalence	40% Prevalence
ratio	Power	Power	Power
1.5	0.55	0.93	0.98
1.8	0.86	0.999	1
2	0.95	1	1
2.5	0.997	1	1

NCI IRB Approval:	October 28, 2004
Protocol Number:	05-C-N021

ANALYSIS OF ALLELE VARIANT GENES AFTER STRATIFICATION BY RACE

We assume 1) a study population of 200 cases and 200 controls, and 2) two-sided alpha = 0.05, and 3) a prevalence of 5%, 20% or 40% for the disease-associated allele. The power to detect an association between an allele variant and cancer risk at a given odds ratio is shown in Table 10.

Table 10

Odds	5% Prevalence	20% Prevalence	40% Prevalence
ratio	Power	Power	Power
1.5	0.35	0.71	0.82
1.8	0.62	0.95	0.99
2	0.76	0.99	0.998
2.5	0.94	1	1

DETECTION OF A GENE-ENVIRONMENT INTERACTION - ANALYSIS OF ALLELE VARIANT GENES AFTER STRATIFICATION BY EXPOSURE

We assume 1) a study population of 400 cases and 400 controls, and 2) two-sided alpha = 0.05, and 3) a prevalence of 20% for the disease-associated allele, and 4) a prevalence of 25% for exposure. We model the control =0, and case=1, and specify the relationship to exposure with a logistic regression model. We categorize exposure into quartiles and assume a linear trend. We will calculate an odds ratio for 4th quartile (highest exposure) compared to first (lowest exposure or baseline). The power to detect an association between an allele variant and cancer risk after stratification for exposure is given in Table 11.

Table 11

Risk Factor	Prevalence	Odds ratio	Power 400/400
Genotype	0.2	1.5	0.93
		1.8	0.999
		2	1
		2.5	1
Genotype + Exposure ¹	0.05	1.5	0.55
		1.8	0.86
		2	0.95
		2.5	0.997

¹4th quartile compared to first

NCI IRB Approval: Protocol Number:

DETECTION OF A GENE-ENVIRONMENT INTERACTION - ANALYSIS OF ALLELE VARIANT GENES AFTER STRATIFICATION BY RACE AND EXPOSURE

We assume 1) a study population of 200 cases and 200 controls, and 2) two-sided alpha = 0.05, and 3) a prevalence of 20% for the disease-associated allele, and 4) a prevalence of 25% for exposure. We model the control =0, and case=1, and specify the relationship to exposure with a logistic regression model. We categorize exposure into quartiles and assume a linear trend. We will calculate an odds ratio for 4th quartile compared to first. The power to detect an association between an allele variant and cancer risk after stratification for exposure (highest versus lowest quartile) is given in Table 12.

Risk Factor	Prevalence	Odds ratio	Power 200/200
Genotype	0.2	1.5	0.71
		1.8	0.95
		2	0.99
		2.5	1
Genotype + Exposure ¹	0.05	1.5	0.35
		1.8	0.62
		2	0.76
		2.5	0.94

Table 12

¹4th quartile compared to first

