5.4.3 DATA ANALYSIS PLAN

ANALYSIS OF GENOTYPES

We will analyze genotype-risk associations in the context of race or other known risk factors of PCa, and will investigate relationships between genotypes and tissue markers, disease progression and poor outcome. If we investigate the association using a priori hypotheses, we will use an unadjusted alpha = 0.05 as the cutoff for significance. If we do not use a priori hypotheses, we will adjust alpha appropriately. An a priori hypothesis would be based on existing knowledge that associates the genotype with cancer risk.

Data analysis will examine PCa occurrence, tumor stage, and outcome, in relation to allele variant genes and known risk factors of PCa. PCa cases will be grouped together and then examined separately by race. Allele variant genes will be categorized (homozygous wild-type, wild-type/mutant, homozygous mutant) for analysis. Other risk factors will also be examined as categorized variables, separated into subgroups of exposure (e.g., dichotomous, tertiles, quartiles). For an analysis by disease stage, we will stratify cases into two subgroups either by pathological stage ($\leq pT2$ versus $\geq pT3$) or by Gleason score (≤ 6 versus ≥ 7). The outcome variables that are studied will be relapse and/or survival. The relationship between PCa and risk factors will be examined by the chi-square test, and by odds ratios with 95% confidence intervals, using the homozygous

NCI IRB Approval:	
Protocol Number:	

October 28, 2004 05-C-N021

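### The power in Tables 9 to 12 is not what 400/400 or 200/200 men give with one control per case, and no power is given for the current 1000/1000 design

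*Protocol*

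**What the plan says.** Protocol section 5.4.2 gives all the inputs. For all cases together (Table 9): "We assume 1) a study population of 400 cases and 400 controls", "two-sided alpha = 0.05", and "a prevalence of 5%, 20% or 40% for the disease-associated allele". For the analysis by race (Table 10): "We assume 1) a study population of 200 cases and 200 controls, and 2) two-sided alpha = 0.05", with the same prevalences. Both tables cover odds ratios of 1.5, 1.8, 2 and 2.5.

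At an odds ratio of 1.5, the printed power at 5/20/40% prevalence is 0.55/0.93/0.98 in Table 9 and 0.35/0.71/0.82 in Table 10. Tables 11 and 12 have columns headed for 400/400 and 200/200. They carry over the 20% column for genotype alone and the 5% column for genotype with exposure (0.20 × 0.25 = 0.05).

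The same section sets the target that these tables support: "The study is designed to detect risk associations that have odds ratios of" 1.5 or more. It also says openly which size the tables belong to: "The power calculation assumes a study size of 400 cases and 400 controls which was the study size in the originally approved protocol". It adds that amendments raised the size to 600/600 in 2006 and 1000/1000 in 2010. Table 7 in section 5.4.1 splits the current target into 500/500 per race. No power is given for 1000/1000 or 500/500.

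**The concern.** With sample size, alpha, prevalence and odds ratio all stated, the power should follow from a standard comparison of two proportions. It does not: the printed values are well above what these samples give.

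Two things depend on this. The design claim about odds ratios of 1.5 or more rests on these tables. And because the protocol says the tables are for a smaller study, a reader will naturally treat them as a floor that 1000/1000 clears comfortably. If the printed values were too high to begin with, that margin is not there, least of all for uncommon variants within each race.

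**Working it through.** **Inputs** (section 5.4.2): n = 400 or 200 cases; an equal number of controls; two-sided alpha 0.05 (critical value 1.96); control prevalence p0 = 0.05, 0.20 or 0.40; odds ratio OR = 1.5, 1.8, 2 or 2.5.

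**Formulas**, with m controls per case:
- case prevalence p1 = OR·p0 / (1 + p0(OR − 1))
- pooled prevalence p̄ = (p1 + m·p0) / (1 + m)
- null standard error s0 = √[p̄(1 − p̄)(1 + 1/m)/n]
- alternative standard error s1 = √[p1(1 − p1)/n + p0(1 − p0)/(m·n)]
- power = Φ[(|p1 − p0| − 1.96·s0) / s1]

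**Worked cell: Table 9, OR 1.5, 20% prevalence, printed 0.93.** p1 = 0.30/1.10 = 0.2727, so the difference is 0.0727.
- As stated (m = 1): p̄ = 0.2364, s0 = 0.0300, s1 = 0.0299. Power = Φ[(0.0727 − 0.0589)/0.0299] = Φ(0.46) = 0.68.
- With m = 400: p̄ = 0.2002, s0 = 0.0200, s1 = 0.0223. Power = Φ[(0.0727 − 0.0393)/0.0223] = Φ(1.50) = 0.93, the printed value.

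**Printed values against three calculations.** The third column is the stated design. The fourth takes 400 (or 200) controls per case. The fifth doubles both groups.

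| Cell | Printed | One control per case | n controls per case | Both groups doubled |
|---|---|---|---|---|
| Table 9, OR 1.5, 5% | 0.55 | 0.28 | 0.55 | 0.49 |
| Table 9, OR 1.5, 20% | 0.93 | 0.68 | 0.93 | 0.93 |
| Table 9, OR 1.5, 40% | 0.98 | 0.81 | 0.98 | 0.98 |
| Table 9, OR 1.8, 5% | 0.86 | 0.54 | 0.86 | 0.83 |
| Table 9, OR 2, 5% | 0.95 | 0.69 | 0.95 | 0.94 |
| Table 9, OR 2.5, 5% | 0.997 | 0.93 | 0.997 | 0.998 |
| Table 10, OR 1.5, 5% | 0.35 | 0.16 | 0.35 | 0.28 |
| Table 10, OR 1.5, 20% | 0.71 | 0.40 | 0.71 | 0.68 |
| Table 10, OR 1.5, 40% | 0.82 | 0.52 | 0.82 | 0.81 |
| Table 10, OR 1.8, 5% | 0.62 | 0.30 | 0.62 | 0.54 |
| Table 10, OR 2, 5% | 0.76 | 0.41 | 0.76 | 0.69 |
| Table 10, OR 2.5, 5% | 0.94 | 0.67 | 0.94 | 0.93 |

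Over all 24 cells of Tables 9 and 10, agreeing to within two points:
- one control per case reproduces 7 cells, all of them printed as 1;
- doubling both groups reproduces 18;
- 400 (or 200) controls per case reproduces all 24, and so does treating the control prevalence as known without error.

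The largest overstatement is 0.86 − 0.54 = 0.32 in Table 9 and 0.76 − 0.41 = 0.35 in Table 10. A simulation of the stated design at OR 1.5 agreed with the formula: 0.273 and 0.678 at 400/400 for 5% and 20% prevalence. Unpooled variance, a continuity correction, a one-sided test, the odds ratio read as a risk ratio, and carriers under a dominant model do not reproduce the tables either.

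**Current design, one control per case, OR 1.5, at 5/20/40%:**
- 1000/1000: 0.58/0.97/0.995
- 500/500 per race: 0.33/0.77/0.89

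**Smallest odds ratio with 80% power, at 5/20/40%:**
- 1000/1000: 1.67/1.35/1.29
- 500/500 per race: 2.02/1.52/1.43

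**The case against.** The strongest defence is that the error no longer does much harm. At 1000/1000 the correct power meets or exceeds every value in Table 9. At 500/500 it meets or exceeds every value in Table 10 except one (OR 1.5 at 5%: 0.33 against 0.35). The original sample size is disclosed, the study is described as exploratory with later validation, and the weak cells are visible in the printed tables: 0.55 pooled and 0.35 per race at 5%, and 0.71 per race at 20%. All of this stands. A reader might infer that the present study is underpowered against its own tables, or that null race-specific findings will be over-read because of them; the figures do not support either.

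The defence does not rescue the tables themselves. Disclosing an old sample size is not the same as disclosing that the power was wrong for that size.

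A reader might also infer that each man was counted twice, once per allele, since doubling the sample matches many cells. The documents do not support this. Doubling misses six cells by 0.03 to 0.08, nothing in section 5.4.2 says alleles were the unit, and section 5.4.3 analyses men by genotype: "Allele variant genes will be categorized (homozygous wild-type, wild-type/mutant, homozygous mutant) for analysis". There is therefore no basis here for asking for a per-allele test.

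**Conclusion.** Wrong as written, and it should be corrected. The printed power overstates what 400/400 and 200/200 men give by up to about 0.32 and 0.35 respectively, and Tables 11 and 12 inherit the error. The likely cause is that the number of controls was entered as the number of controls per case. That is an inference, because the software input is not shown and a control prevalence taken as known fits equally well.

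The consequence for the current study is limited. The enlargement to 1000/1000 roughly delivers the power first printed rather than adding a margin to it. The claim about odds ratios of 1.5 or more holds at 80% power for the pooled analysis at 20% and 40% prevalence, and per race at 40%. It narrowly misses per race at 20% (1.52) and fails at 5% both pooled (1.67) and per race (2.02).

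Assumptions: prevalence means the exposed proportion among controls; the test is an uncorrected two-proportion comparison of men; 80% is the benchmark, since section 5.4.2 names no target power for the genotype analyses.

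**What to change.** Recompute Tables 9 to 12 at 1000/1000 and 500/500 with one control per case, and state that ratio. Tables 9 and 10 would become:

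| Odds ratio | 1000/1000 at 5/20/40% | 500/500 per race at 5/20/40% |
|---|---|---|
| 1.5 | 0.58 / 0.97 / 0.995 | 0.33 / 0.77 / 0.89 |
| 1.8 | 0.90 / >0.99 / >0.99 | 0.63 / 0.98 / 0.996 |
| 2 | 0.97 / >0.99 / >0.99 | 0.79 / 0.998 / >0.99 |
| 2.5 | >0.99 / >0.99 / >0.99 | 0.97 / >0.99 / >0.99 |

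If Tables 11 and 12 keep their present construction, they take the 20% and 5% entries from the same rows. Reword the design statement so that the detectable odds ratio is given by prevalence, separately for the pooled and race-specific analyses.

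The cost is a rewrite of part of section 5.4.2. No subjects, tests or thresholds change. The downside is a power claim that is in places weaker than the present wording.

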We are conducting an epidemiological prostate cancer case-control study in Baltimore, Maryland. Participants will be African-American and Caucasian males who reside in Baltimore city and surrounding areas. The study is ongoing and will recruit 1000 prostate cancer cases and 1000 population-based controls. The cases are recruited at two Baltimore hospitals, the Veterans Affairs Medical Center and the University of Maryland Medical Center. Cases will have pathologically confirmed prostate cancer. The population-based controls are identified through the Maryland Department of Motor Vehicle database, and are frequency-matched by age and race to cases. Enrollment of controls started concurrently with case accrual. The first 12 months of the study constituted a pilot study, during which we evaluated the recruitment procedures. The study involves the administration of a survey and collection of blood from all study subjects. The survey evaluates family cancer history, tobacco use, medication, occupational history, socioeconomic status, and risk factors for prostate cancer. Freshfrozen tumor specimens will be obtained from cancer patients if available. The study is supported by an epidemiological infrastructure that has been developed by our resource contractor at the University of Maryland for a lung cancer case-control study. This lung cancer study is ongoing, and the controls that are recruited for the prostate cancer study are joint controls with the lung cancer study. Hence, population-based male controls recruited by our contractor have double eligibility for the concurrent lung and prostate cancer studies. To achieve an age and race matching of cases and controls in the prostate study, we will over-sample male controls in the lung study.

We will test the primary hypothesis that genes and environmental exposures, including infections and medical history, and interactions between these factors modify prostate cancer susceptibility and contribute to the excessive disease risk among African-American men. As the secondary goal, we will study gene expression profiles of prostate tumors to identify changes in tumor biology that are associated with exposure to genetic and environmental risk factors. It is a focus of this research to identify mechanisms in tumor biology that may cause the aggressive nature of prostate cancer in African-American men.

TABLE OF CONTENTS

1 1.1 1.2	INTRODUCTION STUDY OBJECTIVES BACKGROUND AND RATIONALE	5 7 8

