1.1 STUDY OBJECTIVES

PRIMARY OBJECTIVE

We will examine the association of allele variant genes with PCa risk. The key aim is to examine pathways in relation to PCa, e.g., host defense, inflammation pathways. Within cases, we will examine the relation of genetic variants to molecular, clinical, and prognostic endpoints. The objective will be accomplished with 1) genotype analysis of blood DNA from 1000 cases and 1000 controls and 2) collection of data from questionnaires, medical and pathology records, and the National Death Index. We are testing the hypothesis that susceptibility to nonhereditary PCa is modified by allele variant genes that modulate host defense, inflammation, hormone-stimulated survival and proliferation of mutant cells, the DNA repair capacity, or tumor angiogenesis. The susceptibility may vary by race and lifestyle (gene-environment interaction).

SECONDARY OBJECTIVES

- We will develop gene expression profiles of 60-100 tumors, and will compare gene expression in low-stage and high-stage tumors of African-Americans with gene expression in same stage tumors of Caucasians. The objective is to find gene expression profiles of cancerous and non-cancerous prostate tissue that are characteristic for the disease in African-American men. *We are testing the hypothesis that the molecular signature of primary prostate tumors is different between African-American and Caucasian men. The gene expression profile of African-Americans is associated with an early onset of the disease, a more rapid cancer progression and poor outcome.*
- We will examine the gene expression profiles of tumors from current (n = 10-15) and never smokers (n =10-15). We are testing the hypothesis that current smoking induces a gene signature of tumor progression that reveals the mechanism by which tobacco smoke promotes prostate cancer progression.
- We will determine IGF-1 serum concentrations in our study population and compare gene expression profiles of about 10-15 low-stage tumors from patients with blood IGF-1 levels in the extreme quartiles, respectively. We are testing the hypothesis that a high IGF-1 blood concentration modulates gene expression in primary tumors. The molecular profile is associated with disease progression and poor outcome.

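### Tables 11 and 12 are headed as power for gene-environment interaction but give single-factor association power at 5% joint prevalence, and the protocol states no interaction test

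*Protocol*

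**What the plan says.** Interaction is part of the primary hypothesis. The opening summary says that genes, exposures and "interactions between these factors modify prostate cancer susceptibility", and section 1.1 adds that susceptibility may differ by race and lifestyle, which it calls gene-environment interaction.

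In section 5.4.2 the heading over Table 11 is "DETECTION OF A GENE-ENVIRONMENT INTERACTION - ANALYSIS OF ALLELE VARIANT GENES AFTER STRATIFICATION BY EXPOSURE". A parallel heading, adding race, stands over Table 12. The inputs are "two-sided alpha = 0.05", 20% prevalence of the disease-associated allele, 25% prevalence of exposure, and 400/400 men (Table 11) or 200/200 (Table 12). The text describes a logistic model with exposure in quartiles and a linear trend, and says "We will calculate an odds ratio for 4th quartile (highest exposure) compared to first (lowest exposure or baseline"; a footnote to both tables repeats that contrast. The sentence introducing Table 11 reads "The power to detect an association between an allele variant and cancer risk after stratification for exposure is given in Table 11".

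The same section states that the power tables use the originally approved 400/400, that the target is now 1000/1000 (500/500 per race in Table 7), and that the design aims at odds ratios of 1.5 or more.

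Section 5.4.3 says "PCa cases will be grouped together and then examined separately by race". Regression models are planned to assess associations and adjust for confounders. No product term, heterogeneity test or comparison of stratum odds ratios is named.

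**The concern.** An interaction is a ratio of odds ratios: how far the genotype effect differs between levels of exposure or between races. Its power depends on an interaction odds ratio, the main effects and how exposure is coded. Each row of Tables 11 and 12 has only one prevalence and one odds ratio, so it cannot describe such a test.

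A reader who trusts the headings would believe that the original design had 0.95 power to detect an interaction odds ratio of 2, and that the enlarged study has more. Null interaction results could then be taken as evidence against effect modification when the study was unlikely to see it. Conversely, if stratification is the only route to an interaction, a variant that is significant in one stratum and not in the other may be taken for a real difference.

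**Working it through.** **1. Where the entries come from.** 0.20 x 0.25 = 0.05. For odds ratios 1.5/1.8/2/2.5:

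| Row | Stated power | Equals |
|---|---|---|
| Table 11, Genotype | 0.93/0.999/1/1 | Table 9, 20% column |
| Table 11, Genotype + Exposure | 0.55/0.86/0.95/0.997 | Table 9, 5% column |
| Table 12, Genotype | 0.71/0.95/0.99/1 | Table 10, 20% column |
| Table 12, Genotype + Exposure | 0.35/0.62/0.76/0.94 | Table 10, 5% column |

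All 16 entries match. The joint row is the power for one binary factor of prevalence 5%, that is, exposed carriers against all other men.

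**2. Reproducing the stated figure.** With p0 = 0.05 and p1 = OR x p0/(1 - p0 + OR x p0), the two-proportion power is Φ{[(p1 - p0)√n - 1.96√(2p̄(1 - p̄))]/√[p0(1 - p0) + p1(1 - p1)]}, where p̄ is the mean of p0 and p1.
- n = 400 men per group: 0.275/0.536/0.694/0.926.
- n = 800 alleles per group: 0.487/0.826/0.937/0.998.

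Neither gives 0.55/0.86/0.95/0.997 throughout, nor did any other variant tried. The point does not depend on this, because a single-factor calculation is not interaction power at any n.

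**3. The tables' own contrast.** The genotype effect within quartile 4 alone uses 100 cases and 100 controls. With p0 = 0.20 the same formula gives 0.23/0.43/0.57/0.82. Exposed carriers against unexposed non-carriers in quartile 1 (20% of controls), with the other cells null, gives 0.23/0.44/0.58/0.84. Both fall below Table 11 at every odds ratio.

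**4. Product-term power.** The test is a Wald test of the log interaction odds ratio θ: power = Φ(ln θ/SE - 1.96). With binary exposure, SE² is the sum of the reciprocals of the eight expected cell counts.

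Assumptions, not given in the protocol: genotype and exposure are independent in controls, and main-effect odds ratios are both 1 or both 1.5.

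Worked example, 400/400, quartile 4 versus the rest, main effects 1, θ = 1.5:
- Controls: 400 x (0.60, 0.20, 0.15, 0.05) = 240, 80, 60, 20.
- Cases: 240, 80, 60, 20 x 1.5 = 30; total 410; scaled to 400: 234.1, 78.0, 58.5, 29.3.
- SE² = 0.0833 + 0.0683 = 0.1517, so SE = 0.389.
- ln 1.5/0.389 = 1.04, and Φ(1.04 - 1.96) = 0.18.

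For quartile 4 versus quartile 1, 200 controls remain (80, 80, 20, 20) and about 200 cases (76.2, 76.2, 19.0, 28.6). SE² = 0.125 + 0.1138, SE = 0.489, and power is 0.13. For the quartile trend, SE comes from the information matrix with equally spaced scores and θ as the quartile 4 to quartile 1 ratio; power is 0.14.

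Range over the three codings and both main-effect settings:

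| Cases/controls | θ = 1.5 | 1.8 | 2 | 2.5 |
|---|---|---|---|---|
| 400/400 | 0.13-0.20 | 0.23-0.37 | 0.30-0.48 | 0.47-0.72 |
| Stated, Table 11 | 0.55 | 0.86 | 0.95 | 0.997 |
| 200/200 | 0.09-0.12 | 0.14-0.21 | 0.17-0.27 | 0.27-0.44 |
| Stated, Table 12 | 0.35 | 0.62 | 0.76 | 0.94 |
| 1000/1000 (current) | 0.26-0.42 | 0.48-0.73 | 0.62-0.86 | 0.85-0.98 |
| 500/500 per race (current) | 0.15-0.24 | 0.27-0.44 | 0.36-0.57 | 0.56-0.81 |

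The upper ends come from quartile 4 versus the rest with main effects of 1.5.

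**5. Comparing strata by significance.** Suppose the odds ratio is 1.5 in both races, with 500/500 in each. Power within one race is q = 0.773 at 20% prevalence and 0.331 at 5%. The chance that exactly one race is significant is 2q(1 - q): 2 x 0.773 x 0.227 = 0.35, and 2 x 0.331 x 0.669 = 0.44.

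**The case against.** The sentence above Table 11 does say association, the study calls itself exploratory with later validation, and the text discloses that the tables use a superseded size. Logistic regression is planned and could carry a product term, and model terms are often left to an analysis plan. All of this stands. None of it makes the headings right, and the power is attached to part of the primary hypothesis.

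Four stronger readings are tempting and are not supported:
- **That an interaction test is excluded.** The protocol is silent. It equates detection with stratification and states no test, but it does not rule one out.
- **That power is several-fold too high throughout.** At 400/400 and odds ratio 1.5 the ratio is about 3 to 4 (0.55/0.20 to 0.55/0.13). Set against the current 1000/1000, Table 11 is 1.3 to 2.1 times too high at 1.5 (0.55/0.42 to 0.55/0.26) and nearly right at 2.5.
- **That the rows count each man twice.** Allele counts reproduce the 20% row of Table 11, but not the 5% rows at issue.
- **That a stated power for race differences is too high.** Table 10 claims power for associations within race only. Nor does the protocol say that discordant significance will be read as a difference; the 35% and 44% matter only if someone reads it so.

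**Conclusion.** The point holds in this form. Tables 11 and 12 mislabel single-factor association power, at a joint genotype-and-exposure prevalence of 5%, as power to detect interaction, and they do not match their own quartile contrast either. At the sizes the tables assume, product-term power is below the stated value at every odds ratio. With the current target, power at the design threshold of 1.5 is still only about 0.26-0.42 overall and 0.15-0.24 within race. The enlarged pooled sample does reach about 0.8 or more at an odds ratio of 2 if exposure is coded as the top quartile against the rest, and at 2.5 under all three codings.

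That the rows are not interaction power follows from the tables themselves. The replacement figures rest on independence of genotype and exposure in controls, main-effect odds ratios of 1 to 1.5, and the exposure coding.

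**What to change.** In section 5.4.2, either relabel Tables 11 and 12 as association power for a joint factor and correct the quartile footnote, or replace them with product-term power at 1000/1000 and at 500/500 per race, stating the exposure coding and the assumed main effects.

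In section 5.4.3, add genotype x race and genotype x exposure product terms to the logistic models already planned. Rest any claim that an effect differs by race or exposure on that test and on the ratio of odds ratios with its 95% confidence interval. Keep stratum-specific odds ratios as description.

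The cost is a few model terms and a lower, honest statement of power. No extra subjects or data are needed.
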